7.2. ASSESSMENT OF ELIGIBILITY

The Investigator must assess participant' continued eligibility for the study as per the Inclusion and Exclusion criteria, during the Screening Phase. The eligibility criteria are described in [Section 3.4.1](#) (Inclusion Criteria) and [Section 3.4.2](#) (Exclusion Criteria). In the event that the participant is not suitable or eligible for the study, the participant will be considered "screen failure".

7.2.1. Re-screening

A participant who signed a consent form but did not meet the inclusion/exclusion criteria is classified as a screen failure.

Note: If a participant initially fails to meet inclusion/exclusion criteria and is later reconsidered for participation, the participant will be re-consented and assigned a new unique identification number at the time of re-screening. Participants who fail their first screening attempt may be rescreened a maximum of once and may be enrolled if they are found to meet all inclusion and no exclusion criteria when re-screened.

For consented participants who do not meet eligibility criteria, a Screen Failure Case Report Form (CRF) will be completed. The Screen Failure CRF will contain the following details: the participant identification number, the date of ICF signature, demographic information (see CONFIDENTIAL

Section 7.3), and the reason for screen failure. No additional information will be required for participants who fail screening.

7.3. DEMOGRAPHIC INFORMATION

In this study the demographic information will include:

- Dates of ICF signature
- Date of birth
- Gender
- Race (American Indian or Alaska Native, Asian, Black or African American, Native Hawaiian or Other Pacific Islander, White, Not Reported, or Unknown)
- Ethnicity (Hispanic or Latino, Not Hispanic or Latino, Not Reported, or Unknown)
- Use of tobacco or nicotine replacement products and e-cigarettes

7.4. MEDICAL HISTORY

A medical history will be recorded during the Screening Phase and will include:

- All ongoing medical conditions
- All previously resolved medical conditions that are relevant in the judgment of the Investigator
- Any prior medical conditions that have resolved within the last year

Events that emerge prior to the first treatment will be recorded in the medical history and not as AEs. Aside from being used to determine participant eligibility, this information will permit the Investigator to record the nature, duration, and severity of any ongoing baseline medical conditions prior to the participant's receiving investigational product treatment.

For each relevant history, the following will be documented:

- Disease/disorder/condition
- Date of diagnosis
- History status (resolved or ongoing).

7.5. PHYSICAL EXAMINATION

The physical examination will include routine examinations for the following:

- Constitutional/General Appearance
- Head, Ears, Eyes, Nose, Throat (HEENT)
- Neurologic
- Chest (including heart and lung)
- Abdomen
- Musculoskeletal and Extremities
- Dermatologic
- Lymphatic
- Psychiatric

Each abnormality will be recorded and the Investigator will record an assessment of its clinical significance.

7.6. VITAL SIGNS, HEIGHT AND WEIGHT

The following vital signs will be collected:

- Systolic and Diastolic Blood Pressure
- Pulse
- Respiratory Rate
- Oral Temperature

Blood pressure and pulse will be obtained in the supine position after participant has been resting for 5 minutes.

In addition, the following will be recorded:

- Height (Only performed at Screening visit)
- Weight
- Body Mass Index

7.7. CONCOMITANT MEDICATION

All medications and therapies administered or taken by the participant beginning 14 days prior to Screening Visit and throughout the study will be recorded in the source documents and on the appropriate page of the Case Report Form (CRF). Participants must be questioned at each study

visit concerning any new medications or changes in current medications including over-the-counter medication and topical medication.

For each medication and non-study treatment, the following will be documented:

- Medication/treatment name (generic name may be used if trade name is unknown)
- Dose, unit, and frequency of dosing (individual dosages, not total daily dose).
 - **Note:** *Each new dose of medication should be recorded as a separate entry, with the exception of medications that are given on a sliding scale. For these, it is acceptable to enter the range of the dosage, including the start and stop dates for which the specified dosage range was used.*
- Route of dosing
- Indication for use
- The start date
- The stop date (if medication/therapy is not ongoing).

7.8. CLINICAL LABORATORY ASSESSMENTS

All laboratory assessments will be reviewed by the Investigator. If clinically significant findings, as determined by the Investigator, are recorded for a particular symptom, sign or abnormal measurement, that measurement will be repeated at medically appropriate intervals until the value returns to an acceptable range, a specific diagnosis is established, or the condition is otherwise explained.

Table 7-1: Lab Parameters

CBC Parameters	Biochemistry Parameters	Urinalysis
Hemoglobin (g/dL)	Liver Function Tests	pH
Hematocrit (%)	Total bilirubin (mg/dL)	Specimen Appearance
RBC/Erythrocytes (10 ¹² /L)	Alkaline Phosphatase (ALP) (U/L)	Color
WBC/Leukocytes (10 ⁶ /L)	Aspartate Aminotransferase (AST) (or SGOT) (U/L)	Specific Gravity
Absolute Neutrophil Count (10 ⁶ /L)	Alanine Aminotransferase (ALT) (or SGPT) (U/L)	Ketones
Platelets (10 ⁹ /L)	Total Protein (g/dL)	Bilirubin
Differential WBC: 
 - Neutrophils (%) - Lymphocytes (%) - Monocytes (%) - Eosinophils (%) - Basophils (%) 	Albumin (g/dL)	Occult Blood
	Lactate Dehydrogenase (LDH) (U/L)	Glucose
	Amylase (U/L)	Protein
	Lipase (U/L)	Nitrite
		Urobilinogen (mg/dL)
		Leukocyte Esterase
Miscellaneous	Renal Function Tests	
Serum pregnancy test	Serum creatinine (mg/dL)	
Urine pregnancy test	eGFR(ml/min/1.73 m ²)	
(for female participants of childbearing potential)		
Drug in Urine	Electrolytes	
Alcohol breath test	Sodium (mEq/L)	
Chest X-ray	Potassium (mEq/L)	
PK Evaluation	Chloride (mEq/L)	
ADA	Calcium (mg/dL)	
COVID-19 antigen rapid test at screening and qRT-PCR test	Bicarbonate (mEq/L)	
Serology	Other:	
HBs Ag, HCV Ab and HCV RNA (if required), HIV Ab	Glucose, Random (mg/dL)	
	Creatine kinase (U/L)	
	Triglyceride (TG) (mg/dL)	
	Total Cholesteriol (TC) (mg/dL)	
	Coagulation Parameters	
	Prothrombin time (PT)	
	Activated partial thromboplastin time (APTT)	
	Thrombin time (TT)	
	Fibrinogen (FIB)	

7.9. 12-LEAD ELECTROCARDIOGRAM

12-Lead ECG will be performed per the site standard procedures. The following parameters will be recorded (as part of the participant's medical record) and recorded on the appropriate page of

the CRF: ventricular rate (beats per minute), PR interval (msec), QRS interval (msec), QT interval (msec), and QTc interval (msec). Additionally, the Investigator will record the overall results of the 12-lead ECG reading as either normal or abnormal, and if abnormal, as either “not clinically significant” or “clinically significant.” If abnormalities are observed, each will be recorded. Each treatment-emergent abnormality that is clinically significant will be recorded as an AE. Each 12-lead ECG should be signed by a physician. Clinically significant abnormal 12-lead ECG’s may be repeated at the discretion of the Investigator.

7.10. NASOPHARYNGEAL SWAB OR NASAL SWAB FOR COVID-19

Nasopharyngeal or nasal swab sample will be collected for COVID-19 antigen rapid test at screening and qRT-PCR test according to Table 4-1 and Table 4-2. The participant will be followed, and samples will be collected for the entire duration of the study.

7.11. SPIROMETRY ASSESSMENT

It is to be used as a validation method to ensure participants don’t have a former yet undiagnosed respiratory disease and to validate the presence of abnormal Forced Expiratory Volume1(FEV1) values.

Spirometry will evaluate the respiratory functions of acute bronchospasm. Spirometric parameter including FEV1% (the percent of predicted FEV1), FEV1/FVC, and peak expiratory flow (PEF).

Extra spirometry assessments may be repeated at the discretion of the investigator.

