2.2. STUDY OUTCOME MEASURES

2.2.1. Primary Outcome Measures

The primary outcome measures in this study are:

- Evaluation of the safety and tolerability of MBS-COV after a single and multiple dose administrations in healthy participants. The following parameters will be used to assess safety:
 - Incidence and severity of Treatment-Emergent Adverse Events (TEAEs)
 - Incidence of withdrawals due to Adverse Events (AEs)
 - Incidence of Treatment-Related Adverse Events
 - Incidence of Serious Adverse Events (SAEs)
 - Change/shifts in laboratory values from baseline
 - Change in vital signs including blood pressure, pulse, respiratory rate, and temperature from baseline
 - Change in spirometry from baseline to assess the acute bronchospasm
 - Change in other safety examination parameters from baseline

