Results at each scheduled visit will be recorded on the CRF.

Spirometry assessment

Spirometry assessment will include FEV1%, FEV1/FVC, PEF.

Results at each scheduled visit will be recorded on the CRF.

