7.1. General Statistical Consideration

If no other specified, SAS® (Version 9.4 or above) statistical software will be used for all statistical calculation and all analyses of safety part.

All summaries will be provided by treatment group for both study parts. Continuous variables will be summarized using descriptive statistics including number of observations (n), mean, standard deviation, median (med), minimum (min) and maximum (max). Categorical variables will be summarized using frequency and percentages.

For laboratory examination, keep 2 decimal places for mean, minimum, median, and maximum, 3 decimals for standard deviation. For percentage, keep 1 decimal place.

If no other specified, baseline of safety analysis is defined as the last effective assessment record before first treatment dosing.

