7.2.2. Derivation and Transformation on Data

Apart from the calculation of study endpoints mentioned in section 4, which are based on data collected via CRF, no derivation or transformation will be done for data. Outliers will be reported to data management function as data issue to be resolved or confirmed before database lock. No other special data handling will be done.

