7.4.7. Spirometry Assessment

Spirometry results of each visit and their changes from baseline will be calculated and summarized by treatment group.

Listing by subject will be provided for all spirometry assessment results. Abnormal with clinical significance results of spirometry assessment will be provided by listing separately.

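### Spirometry is a primary outcome for acute bronchospasm, but no planned output scales a participant's FEV1 fall to their own baseline, combines the four post-dose readings, or counts falls by dose when they are not judged adverse events

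*Protocol*

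**What the plan says.** Protocol 2.2.1 lists among the primary outcome measures: "Change in spirometry from baseline to assess the acute bronchospasm". SAP 4.1.1 and 4.2.1 repeat this for Parts A and B. Protocol 7.11 names the measures: "Spirometric parameter including FEV1% (the percent of predicted FEV1), FEV1/FVC, and peak expiratory flow (PEF". SAP 4.3.2 agrees: "Spirometry assessment will include FEV1%, FEV1/FVC, PEF". Absolute FEV1 in litres is not named.

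SAP 7.4.7 plans three outputs:
- Group summaries: "Spirometry results of each visit and their changes from baseline will be calculated and summarized by treatment group".
- A listing, participant by participant, of every spirometry reading.
- A further listing restricted to findings judged important: "Abnormal with clinical significance results of spirometry assessment will be provided by listing separately".

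The general summary statistics in SAP 7.1 are n plus "mean, standard deviation, median (med), minimum (min) and maximum (max". SAP 7.2.2 says that "no derivation or transformation will be done for data", but the same sentence first exempts the calculation of the endpoints in SAP section 4.

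Readings are scheduled 5, 15, 30 and 60 minutes after dosing, on Day 1 in Part A and on each of the seven dosing days in Part B (Protocol Tables 4-1 and 4-2; 4.2.3, 4.3.3, 4.3.4). Baseline is the last valid record before first dosing (SAP 7.1). It may be up to 7 days old (Protocol 4.2.1 and 4.3.2), because no spirometry is scheduled before dosing on Day 1. Inclusion criterion 5 requires FEV1% of at least 80 and sets no upper limit.

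**The concern.** Bronchospasm shows as a fall in one person's FEV1 relative to that person's own starting value. The planned group summary works on a different scale (change in percent-predicted points) and at a different level (the group). Neither document defines a relative fall, a largest post-dose fall, a numeric criterion for a clinically significant spirometry result, or a count of participants with a fall. SAP 7.4.7 also speaks of results at each visit without saying how the four post-dose readings become one result.

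At stake is whether a primary outcome of a first-in-human inhaled trial reports what it was included to show: how many participants at each dose had a material fall in FEV1. With 6 or 8 active participants per cohort, a real signal may well appear as a single case.

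**Working it through.** **1. Group sizes.** Part A has 3 cohorts of 6 active and 2 placebo; Part B has 2 cohorts of 8 active and 2 placebo. 3 × (6 + 2) + 2 × (8 + 2) = 44, which reproduces the stated sample size. The documents give no figure for bronchospasm, for the SD of change, or for the spread of baseline FEV1%. Those values below are assumptions.

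**2. Points against relative fall.** Relative fall = points lost / baseline.
- 16/80 = 20%, but 16/120 = 13.3%.
- A 20% fall is 0.20 × 80 = 16 points, or 0.20 × 120 = 24 points.

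Equal point changes therefore differ in severity across baselines that the entry criterion allows.

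**3. The relative fall can be computed from planned data.** FEV1% = 100 × FEV1/predicted. Predicted FEV1 is constant within a participant over the study, so it cancels: (post − baseline)/baseline is the same in FEV1% as in litres.

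**4. Dilution in the group summary.** Let one participant fall by a fraction r from baseline b, with no change in the other n − 1. The mean change is −r × b/n, the median is 0 and the minimum is −r × b.

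| Assumed fall | Points | Mean, n = 6 | Mean, n = 8 | Minimum |
|---|---|---|---|---|
| 20% from 80 | 16 | −2.7 | −2.0 | −16 |
| 20% from 95 | 19 | −3.2 | −2.4 | −19 |
| 20% from 120 | 24 | −4.0 | −3.0 | −24 |

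Over assumed falls of 10% to 30% and baselines of 80 to 120, the mean runs from −1.3 to −6.0 (n = 6) or −1.0 to −4.5 (n = 8). The minimum shows the full −8 to −36. The mean and median hide the case; the minimum does not. The minimum is, however, one number per group. It cannot separate one affected participant from three, and it is not scaled to baseline.

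**5. How often one case would be seen.** The chance of at least one event is 1 − (1 − p)^n. For assumed true risks of 5%, 10% and 20% it is 26.5%, 46.9% and 73.8% with n = 6, and 33.7%, 57.0% and 83.2% with n = 8. A count would report one case as 1/6 (16.7%, exact 95% CI 0.4% to 64.1%) or 1/8 (12.5%, 0.3% to 52.7%).

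**6. Noise in a largest-fall table.** Assume normal changes with SD 5 points, baseline 100, no drug effect and independent readings. The chance that one reading passes a 10% cut is Φ(−10/5) = 0.0228.
- One dosing day, 4 readings: 1 − (1 − 0.0228)^4 = 8.8%.
- Seven days, 4 × 7 = 28 readings: 1 − (1 − 0.0228)^28 = 47.5%.

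| Cut | 4 readings, SD 5 (SD 3 to 7) | 28 readings, SD 5 (SD 3 to 7) |
|---|---|---|
| 10% | 8.8% (0.2% to 27.3%) | 47.5% (1.2% to 89.3%) |
| 15% | 0.5% (<0.1% to 6.3%) | 3.7% (<0.1% to 36.5%) |
| 20% | <0.1% (<0.1% to 0.9%) | 0.1% (<0.1% to 5.8%) |

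Readings that share one baseline are correlated, so independence is a simplification and these are rough figures.

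**The case against.** A reader might infer that bronchospasm is analysed only through group change in FEV1%, and that one case would be averaged out of sight. The documents do not support this. FEV1/FVC and PEF are also summarised. SAP 7.4.7 lists every participant's results and separately lists clinically significant ones. The minimum is among the general statistics in SAP 7.1.

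The adverse-event route matters too. Incidence and severity of TEAEs is itself a primary outcome, and SAP 7.4.2 counts participants by preferred term and treatment group. Bronchospasm reported as an adverse event is therefore already counted by dose. What remains is a fall not judged an adverse event. Protocol 9.1 directs clinically significant examination and laboratory findings to adverse-event reporting, and 7.9 does so for ECG; 7.11 has no such sentence for spirometry. The toxicity scale in Appendix 1 has no FEV1 or PEF row.

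A reader might also infer that SAP 7.2.2 forbids a percent fall. Its exception for section 4 endpoints arguably covers one, so the text is unclear rather than a bar. It would also be tempting to ask how often the active-minus-placebo mean would detect one case. That is beside the point, because the plan has no inferential test and no formal hypothesis.

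Finally, cut-points are a choice, and a largest fall measured against an old baseline picks up noise. Both objections stand, and both shape the fix.

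**Conclusion.** The point holds in a limited form. A large drop would be visible in the planned output, and a reported bronchospasm would be counted. What is missing is a participant-level summary of a primary outcome: no relative fall, no rule for combining the four readings, and no count by dose of falls not judged adverse events. Identifying those falls rests on investigator judgment and on reading listings.

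The 6- to 8-fold dilution of the mean follows from the cohort sizes alone. The 20% against 13% contrast follows from the open upper limit on baseline FEV1%, with 120 taken as an example. The noise rates rest on the assumed SD, baseline and independence, and change sharply with SD. The change is worth making before unblinding. It does not call the raw data or the planned listings into question.

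**What to change.** In SAP 7.4.7, derive percent change in FEV1 = 100 × (post-dose FEV1% − baseline FEV1%)/baseline FEV1%. For each participant and dosing day, take the largest fall over the 5-, 15-, 30- and 60-minute readings. Tabulate by treatment group, with placebo alongside, the number and percentage of participants whose largest fall reaches reporting cut-points that the sponsor fixes before unblinding, for example 15% and 20%. Report Part B by dosing day as well as overall, and list the individual values.

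If a 10% cut is kept, add a note that the worst of repeated readings against a baseline up to 7 days old will cross it by noise, and read it only beside placebo. State in SAP 7.2.2 that this derivation falls under the section 4 exception. Keep the planned summaries and listings.

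The cost is one derived variable and one table from data already scheduled, plus agreement on cut-points before unblinding. The cut-points are for reporting only and are not management rules.

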7.12. RANDOMIZATION

Healthy participants who are eligible to participate in the study will be randomized to one of the treatment groups via IWRS in assigned cohort (Interactive Web Based Randomization System) prior to IP administration.

8. STATISTICAL CONSIDERATIONS

This section presents general information about statistical considerations and concepts such as randomization, sample size, and a brief discussion on analysis methodology, as well as some data conventions. Detailed descriptions of the statistical analysis methods and data conventions will be included in a separate document; i.e., the Statistical Analysis Plan (SAP).

8.1. COHORTS/TREATMENT GROUPS

Refer to [Table 3-1](#), and [Table 3-2](#) for description of cohorts/treatment groups.

8.2. STUDY ENDPOINTS/ OUTCOME MEASURES

Refer to [Section](#) for list of study endpoints/outcome measures.

8.3. SAMPLE SIZE DETERMINATION AND RATIONALE

The sample size of at least 44 participants (24 healthy participants in part A and 20 healthy participants in part B) will be used in this study. This sample size is selected based on clinical judgment and not based on statistical power calculation; it is deemed adequate to provide clinically meaningful descriptive results consistent with study objectives.

8.4. RANDOMIZATION

In Part A (SAD Phase), 24 participants (8 per group) will be randomized in a 6:2 ratio (MBS-COV: placebo). In Part B (MAD Phase), a total of 20 participants (10 per group) will be randomized in a 8:2 ratio (MBS-COV: placebo)

An individual, independent of the clinical study team, will develop the randomization schedules. The actual randomization assignment will be made through a web based system. Participants who have provided written informed consent and have met all the inclusion criteria and none of the exclusion criteria will be randomized to one of the treatment groups.

8.5. BLINDING AND PREVENTION OF BIAS

8.6. INTERIM ANALYSIS

There is no efficacy interim analysis planned for this study; however, the safety data from all participants of each completed cohort will be reviewed by the SRC prior to enrolment of further participants or dose escalation.

8.7. GENERAL STATISTICAL CONSIDERATIONS

All collected study data will be presented in participant data listings and/or will be summarized. Statistical analyses will be performed using SAS® for Windows, version 9.4 or later.

A Statistical Analysis Plan (SAP) will be developed and approved before the database is locked. The SAP will present the detailed statistical methodology to be used in analyzing the efficacy and safety data from this study.

8.7.1. Statistical Analysis Populations

8.7.1.1. Full Analysis Set (FAS)

FAS includes all randomized participants. This analysis set will be used to analyze the disposition, demographic and baseline characteristics of the subjects.

8.7.1.2. Safety Set (SS)

SS includes all the participants who receive the study drug at least once. This population will be used for the analysis of safety parameters.

8.7.1.3. PK concentration analysis set (PKCS)

PKCS includes all randomized participants who receive at least one dose of the study drug and have at least one plasma concentration. The PKCS will be used for PK concentration analysis.

8.7.1.4. PK parameters analysis set (PKPS)

PKPS includes all randomized participants who receive at least one dose of the study drug with no major protocol violations or protocol deviations that have a significant impact on PK parameters (C_{max} , AUC, etc.), and have at least one analyzable PK parameter. The PKPS will be used for PK parameters analysis.

8.7.1.5. Immunogenicity Set (IS)

IS includes all randomized participants who receive at least one dose of the study drug, and have at least one ADA concentration. The IS will be used for immunogenicity analysis.

8.7.2. Missing Data

All efforts will be made to minimize the amount of missing data for the study. The methods of handling missing data will be detailed in the SAP.

8.7.3. Statistical Methods

All safety analyses will be conducted using the Safety population.

For continuous variables, descriptive statistics (n, mean, standard deviation, median, minimum and maximum) will be presented by treatment group. For categorical variables both frequencies and percentages will be presented by treatment group.

8.7.4. Participant Disposition

The disposition of all participants who signed an ICF will be provided. The numbers of participants screened, randomized (if applicable), received treatment, completed, and discontinued during the study, as well as the reasons for discontinuation will be summarized. Disposition and reason for study discontinuation will also be provided as a by-participant listing.

